List of Abbreviations

Abbreviation	Definition		
AE	Adverse Event		
AIS	Acute Ischemic Stroke		
CRA	Clinical Research Associate		
CRO	Contract Research Organization		
CRF	Case Report Form		
СТ	Computed Tomography		
СТА	Computed Tomography Angiography		
DSA	Digital Substraction Angiography		
EC	Ethics Committee		
EDC	Electric Data Capture		
eTICI	Extended Thrombolysis in Cerebral Infarction		
GCS	Glasgow Coma Scale		
ICF	Informed Consent Form		
MRA	Magnetic Resonance Angiography		
MRI	Magnetic Resonance Imaging		
mRS	Modified Rankin Scale		
NIHSS	National Institute of Health Stroke Scale		
PI	Principal Investigator		
SAE	Serious Adverse Event		

Protocol Synopsis

Sponsor	The First hospital Affiliated to Naval Medical University(Changhai hospital)			
Protocol No.	PROTECT-MT			
Study Title	PROximal TEmporary oCclusion using balloon guide caTheter for Mechanical Thrombectomy (PROTECT-MT)			
Study Design	A prospective, multicenter, randomized controlled, open-label, blinded outcome evaluation (PROBE) trial			
Study Population	Subjects with acute ischemic stroke(AIS) due to anterior circulation large vessel occlusion(LVO), and are eligible for mechanical thrombectomy(MT) according to local guidelines			
Study Objective	To determine the effectiveness of balloon guide catheter(BGC) as compared to standard guide catheter on functional outcome (modified Rankin Scale [mRS] score) in patients with acute ischemic stroke due to anterior circulation large vessel occlusion.			
Number of planed Sites	40-60 centers			
Inclusion/Exclusion Criteria	 Inclusion Criteria To be eligible for inclusion for this study, subjects are to satisfy all of the following criteria: 1) Age ≥18 years. 2) Diagnosis of AIS with confirmed anterior circulation LVO (including intracranial segment of the internal carotid artery, and the first or proximal second segment [M1 or proximal M2] of the middle cerebral artery) by brain imaging. 3) To receive MT within 24 hours after AIS onset according to local guidelines. 4) Preoperative mRS score of 0-1. 5) Signed informed consent form obtained from the subject (or approved surrogate). Exclusion Criteria Subjects who meet any of the following criteria should be excluded from this study: 1) Intracranial hemorrhage confirmed by imaging. 2) Known or suspected pre-existing (chronic) large vessel occlusion in the symptomatic territory. 3) Excessive vascular access tortuosity disables the use of balloon guide catheter. 4) Intracranial stent implanted in the symptomatic territory that precludes the deployment/removal of the mechanical thrombectomy device. 5) Any other condition that precludes the performing of mechanical thrombectomy procedure. 			

PRØIECT-MT

	6) Occlusions in multiple vascular territories confirmed by Computed
	Tomography Angiography(CTA) or Magnetic Resonance Angiography(MRA).
	7) Subjects who are pregnant.
	8) Subjects who are allergy to the contrast agent.
	9) Subjects who refuse to cooperate or unable to tolerate interventional operation.
	10) Subjects whose expected lifetime are less than 90 days.
	 Subjects who are unlikely to participate in follow-up assessments according to the investigator's judgement.
	12) Any other condition that, according to the investigator's judgement, not suitable for using of balloon guide catheter.
	1. Randomization:
	After confirmation of eligibility, subjects will be randomized via an Internet- based randomization system in a 1:1 manner to treatment with BGCs(Intervention group) or not(control group), stratified by site, preferred thrombectomy strategy(stent retriever VS aspiration VS stent retriever + aspiration), and onset to randomization time(<6 hours VS \geq 6 hours)
	2. Group Assignment:
	Subjects will be treated with thrombectomy based on the results of randomization.
	Intervention group: Subjects treated with BGCs combined with conventional thrombectomy.
	Control group: Subjects treated with standard guide catheter combined with conventional thrombectomy.
Randomization, Group Assignment, and Blinding	Any National Medical Products Administration (NMPA) devices (including the use of a thrombectomy stent, distal aspiration catheter, or combine use of both) are allowed.
	3. Blinding:
	Both patient and treating physician will be aware of the treatment assignment. But outcome evaluation would be blinded. Information on outcome at 90 days will be assessed through standardized forms and procedures, by a trained investigator blinded for treatment allocation. Interviews will be recorded. Assessors who are blinded to the treatment allocation will perform assessment of outcome on the modified Rankin scale on this information. Results of neuro-imaging will be also assessed in a blinded manner. Information on treatment allocation will be kept separate from the main study database. The steering committee will be kept unaware of the results of interim analyses of efficacy and safety. An independent DSMB statistician will combine data on treatment allocation with the clinical data in order to report to the data monitoring committee (DSMB).
	1. Primary Outcomes
Study Outcomes	Functional outcome, defined as modified Rankin Scale (mRS) score shift at 90 days (± 14 days).
	2. Secondary Outcomes

PRØIECT-MT

		1)	
		1)	versus 3-6, 0-3 versus 4-6, 0-4 versus 5-6, 0-5 versus 6).
		2)	Change in stroke severity (NIHSS score) at 24 hours post treatment.
		3)	Change in stroke severity (NIHSS score) at 7 days post treatment or discharge (whichever occurs first).
		4)	Final infarction volume at 5-7 days post treatment.
		5)	Technical success rate (defined as successfully navigating the guide catheter into the target vessel, and finishing the mechanical thrombectomy procedure without changing to another guide catheter).
		6)	Reperfusion outcome (eTICI 2b or greater, eTICI 2c or greater, eTICI 3) in final angiogram.
		7)	Reperfusion outcome (eTICI 2b or greater, eTICI 2c or greater, eTICI 3) after the first pass.
		8)	Time from groin puncture to successful reperfusion (eTICI 2b or greater, eTICI 2c or greater).
		9)	Percentage of subjects with acceptable revascularization quality (eTICI 2b or greater, eTICI 2c or greater) within 45 min of access.
	10) Number of thrombectomy attempts (final).		Number of thrombectomy attempts (final).
		11)	Occurrence of emboli to a new territory.
	3.	Safe	ety Outcomes:
		1)	Deaths at 90 days (±14 days) post treatment.
		2)	Intracranial hemorrhage, symptomatic intracranial hemorrhage or asymptomatic intracranial hemorrhage at 7 days post treatment or discharge (whichever occurs first).
		3)	Other serious adverse events (SAEs) adjudicated by the Clinical Events Committee.
		4)	Any peri-procedural complications, including vessel dissection, arterial perforation, and femoral access complications, etc.
	4.	Cos	t Outcomes:
		1)	Health-related quality of life evaluated using EQ-5D.
		2)	Utility-weighted mRS score.
		3)	Duration of hospitalization.
		4)	Treatment cost.
	•	Ba	seline
	•	24	hours (±12 hours) post treatment
Study visits	•	7 d	ays (±2 days) post treatment or at discharge
	•	90	days (±14 days) post treatment
	•	Sa	mple Size
Statistical Analysis	We tria	base 1, wh	ed our estimations on the distribution of the mRS in the control group of the nich we derived from the intervention group of the MR CLEAN trial: mRS0:

3%; mRS 1: 9%; mRS 2: 21%; mRS 3: 18%; mRS 4: 22%; mRS 5: 6% and mRS 6:21%. Based on previous studies, we assumed a favorable treatment effect with a common odds ratio (cOR) of 1.43, corresponding to an 8% absolute increase in the rate of mRS scores of 0-2. In a simulation with 5000 runs we computed the proportion of positive trials, for a given sample size. A sample size of 920 was determined to detect the superiority with a power of 87% and two-sided alpha of 0.05. Considering 5% dropout rate and 5% crossover rate, a final sample size of 1074, 537 per arm, would be needed.

• Methods for Statistical Analysis

Analyses will be performed using the intention-to-treat (ITT) principle.

Statistical analysis will be detailed in a pre-specified Statistical Analysis Plan (SAP).

Two interim analyses would be performed when 30% and 60% of the 90-day followup data have been collected.

1 Study Background

Stroke has become the leading cause of death and adult disability in China ^[1]. According to Stroke Prevention and Treatment Report of China in 2019, there are 12.42 million stroke cases in people aged 40 years or above in China, 65% of whom are ischemic stroke. With population aging, stroke prevalence is continuously rising, bringing a heavy burden to the families and society ^[2].

The key to the treatment of acute ischemic stroke (AIS) is to recanalize the occluded vessels as early as possible and save the brain tissue around the core infarct area, namely the ischemic penumbra. With the publication of five randomized controlled trials comparing Endovascular treatment (EVT) with standard medical treatment in 2015 ^[3-7], EVT combined with intravenous thrombolysis has become the preferred treatment for patients with large vessel occlusion of anterior circulation within 6 hours of onset ^[8]. Subsequently, the DAWN and DEFUSE 3 studies in 2018 further extended the treatment time window to 24 hours ^[9, 10]. Although mechanical thrombectomy has significantly improved the successful recanalization rate in patients with acute ischemic stroke due to large vessel occlusion, a large proportion of patients still have poor clinical prognosis. How to improve the prognosis of these patients remain a clinical problem needed to be solved.

The Balloon Guide Catheter(BGC) is device used during mechanical thrombectomy, which offers proximal flow control and a stable platform to facilitate the insertion and guidance of an intravascular catheter. Dilation of the balloon during the procedure would enable a significant flow arrest or reversal, and hence reduce the risk of thrombus fragmentation and distal embolism ^[11]. Some observational studies ^[12-17] have shown that the use of balloon guide catheter could improve the quality of final reperfusion, shorten the procedure time, and may lead to better clinical outcomes in patients undergoing thrombectomy. In a retrospective study involving 955 patients, the final and first-pass reperfusion rates (mTICI 2b or 3) were 86.8% and 37.0% in BGC group, which were higher than those in the standard guide catheter group, i.e 74.7% and 14.1% (P<0.001). Thrombectomy maneuvers (2.5 ± 1.9 versus 3.3 ± 2.1 ; P<0.001) and procedure time (54.3 ± 27.4 min vs 67.6 ± 38.2 min; P<0.001) were significantly decreased in BGC group compared with those in standard guide catheter group. In multivariate analysis, BGC usage was an independent factor for good clinical outcome (odds ratio: 1.40; 95% CI, 1.02 1.92; P = 0.038) ^[16]. In another prospective registry study, STRATIS (Systematic Evaluation of Patients Treated With Neurothrombectomy Devices for Acute Prevention Stroke), the first recertification ($\geq 2c$

and $\geq 2b$) rates of three guide catheter(BGC, standard guide catheter, distal access catheter) were (212/443 [48%] vs 16/62 [26%] vs 83/235 [35%]), and (294/443 [66%] vs 26/62 [42%] vs 129/234 [55%]), respectively. The first recanalization rate of BGC group was higher than that of distal access catheter and standard guide catheter, and the clinical prognosis of patients in the balloon guide catheter group was also better than that of the other two groups, and the rates of functional independence were 253/415 [61%] vs. 23/55 [42%] vs. 113/218 [52%] ^[14].

However, controversies existed regarding the use of balloon guide catheter. For example, Bourcier R et al reported that balloon-guide catheter may be unnecessary with used with a combination of aspiration catheter and stent, and the rates of recanalization (60.1% VS 62.7%; RR, 0.92; 95%CI, 0.80-1.14) and functional outcome (44.6% Vs 40.0%; RR 1.12, 95%CI, 0.85-1.47) were similar between BGC group and standard guide catheter group ^[18]. In addition, some technical issues may hinder the widespread use of balloon guide catheters. The stiffness and trackability of the catheter may result in complications, also preparing and delivering the BGCs may prolonged procedure time and increase of the cost of the procedure ^[19]. These issues have aroused debates on whether balloon guide catheter should be routinely used in thrombectomy treatment, which led to absence of standardized procedures for thrombectomy^[20, 21].

Because of the above reasons, there is an urgent need for a high-quality randomized trial to assess the effectiveness of BGC in thrombectomy for acute stroke due to large vessel occlusion and to standardize the procedure of mechanical thrombectomy. We aimed at establishing the best thrombectomy technique and procedure for AIS due to LVO, so as to improve the clinical prognosis, and reduce the national economy burden.

2 Study Objective

The objective of this study is to determine the effectiveness of balloon guide catheter(BGC) as compared to standard guide catheter on functional outcome (modified Rankin Scale [mRS] score at Day 90) in patients with acute ischemic stroke due to anterior circulation large vessel occlusion.

3 Study Design

This is a prospective, multicenter, randomized controlled, open-label, blinded outcome assessment trial involving 1074 eligible subjects to be recruited from 40-60 hospitals in China.

Subjects who meet the eligibility criteria will be randomized to either intervention group (receiving treatment with BGC) or control group (receiving treatment with standard guide catheter). Followed up would be conducted at 1 day, 7 days, and 90 days after thrombectomy.

Study design is presented as below (Figure 1).

Figure 1. Study schema

4 Study Population

Subjects who are with AIS due to LVO of the anterior circulation confirmed by cranial imaging and judged to be eligible for being treated with mechanical thrombectomy according to local guidelines will be enrolled into this study. The principal investigator at each site will be responsible for subject screening and enrollment.

4.1 Inclusion Criteria

To be eligible for inclusion for this study, subjects are to satisfy all of the following criteria:

- 1) Age ≥ 18 years.
- Diagnosis of AIS with confirmed anterior circulation LVO (including intracranial segment of the internal carotid artery, and the first or proximal second segment [M1 or proximal M2] of the middle cerebral artery) by brain imaging.
- 3) To receive MT within 24 hours after AIS onset according to local guidelines.
- 4) Preoperative mRS score of 0-1.

5) Signed informed consent form obtained from the subject (or approved surrogate).

4.2 Exclusion Criteria

Subjects who meet any of the following criteria should be excluded from this study:

- 1) Intracranial hemorrhage confirmed by imaging.
- Known or suspected pre-existing (chronic) large vessel occlusion in the symptomatic territory.
- 3) Excessive vascular access tortuosity disables the use of balloon guide catheter.
- 4) Intracranial stent implanted in the symptomatic territory that precludes the deployment/removal of the mechanical thrombectomy device.
- 5) Any other condition that precludes the performing of mechanical thrombectomy procedure.
- 6) Occlusions in multiple vascular territories confirmed by Computed Tomography Angiography(CTA) or Magnetic Resonance Angiography(MRA).
- 7) Subjects who are pregnant.
- 8) Subjects who are allergy to the contrast agent.
- 9) Subjects who refuse to cooperate or unable to tolerate interventional operation.
- 10) Subjects whose expected lifetime are less than 90 days.
- 11) Subjects who are unlikely to participate in follow-up assessments according to the investigator's judgement.
- 12) Any other condition that, according to the investigator's judgement, not suitable for using of balloon guide catheter.

4.3 Subject Withdrawal Criteria

While study withdrawal is discouraged, subjects may withdraw from the study at any time, with or without reason and without prejudice to further treatment. Withdrawn subjects will not undergo any additional follow-up, nor will they be replaced, but the collected data may be used for statistical analysis. Such withdrawal, including the reason for withdrawal, should be documented in the patient's file.

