6.1 Study Outcomes

6.1.1 Primary Outcomes

The primary outcome is functional outcome, defined as modified Rankin Scale (mRS) score shift at 90 days (±14 days).

The modified Rankin Scale (mRS) is an ordinal hierarchical scale ranging from 0 to 5, with higher scores indicating more severe disability. A score of 6 has been added to signify death.:

0 = No symptoms;

1 = Symptoms, no disability: Minor symptoms that do not interfere with lifestyle;

15 / 43

- 2 = Slight disability: Slight disability, symptoms that lead to some restriction in lifestyle, but do not interfere with the patient's capacity to look after himself.;
- 3 = Moderate disability: Moderate disability, symptoms that significantly restrict lifestyle and prevent totally independent existence;
- 4 = Moderately severe disability: Moderately severe disability, symptoms that clearly prevent independent existence though not needing constant attention;
- 5 = Severe disability, totally dependent patient requiring constant attention day and night.
- 6 = Death.

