7.2 Methods for Statistical Analysis

Analyses will be performed based on the intention-to-treat (ITT) principle. Baseline data by treatment allocation will be reported with statistical procedures. Missing values for baseline

characteristics will be reported. Missing baseline characteristics will be imputed using regression imputation as appropriate. The primary outcome will be analyzed by means of an ordinal logistic regression. Pre-defined subgroups will be analyzed by testing for interaction between the specific baseline characteristic and treatment. Any reported SAE or discontinuation of assigned treatment due to an SAE will be classified using MedDRA.

Statistical analyses will be detailed in the pre-specified Statistical Analysis Plan (SAP).

The study consists of 2 interim analyses to be performed when 30% and 60% of the 90-day follow- up data have been collected. The independent data and safety monitoring board (DSMB) will adopt the Haybittle-Peto rule, and $\alpha < 0.001$ in the interim analysis will be considered as statistically significant. Because only 2 interim analyses will be performed, the conventional significance level ($\alpha = 0.0482$) will be used for final analysis. The DSMB will monitor SAEs (e.g. death, spontaneous intracerebral hemorrhage [sICH], and neurological deterioration) periodically, and the occurrence of excessive SAEs will trigger discussion regarding termination of the study.

8 Study Monitoring

Qualified Clinical Research Associates (CRAs) will be responsible for regular monitoring of this study according to the monitoring plan. The monitoring is to ensure that all parties involved in the clinical study comply with the requirements in the Good Clinical Practice (ICH-GCP/GCP) and other applicable regulations during the implementation of the study, to protect the rights of the subjects and ensure the compliance with the clinical study protocol/procedures, as well as the authenticity, completeness and accuracy of the collected data.

Monitoring procedures include one or more visits before study initiation, regular monitoring visits during the study according to the agreed frequency of monitoring, and monitoring visits related to site closure after the end of the study.

9 Data Management

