2.2.1 Intention-to-treat Population

The ITT population will include all randomized subjects according to ITT principles, regardless of their eligibility and any protocol deviations, in which subjects will be analyzed according to the group assigned by randomization. ITT is the primary efficacy analysis set for this study and will also be used for analyses of demographics, baseline characteristics, medical history and concomitant medication information.

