2.4.2 Missing data

We will report proportions of missing values for all collected variables where needed.

Missing baseline characteristics data will be imputed by regression interpolation as appropriate.

If there is a large number of missing data on efficacy and safety, an evaluation on the missing data should be conducted before formal analysis, and the study team will propose and determine the solution before database lock.

For subjects who died within the study period, the worst scores will be assigned for all subsequent not-assessed clinical outcome measures in their analyses, as follows (Table 3).

Clinical outcomes	The worst scores
mRS	6
NIHSS	42

Table 3. The worst scores of clinical outcomes

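### Follow-up ends completely at withdrawal, with no limited-contact or vital-status option, so some 90-day mRS scores go uncollected and the SAP names no method for handling them

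*Protocol*

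**What the plan says.** Protocol 4.3 allows withdrawal from the study as a whole and describes no partial form: "While study withdrawal is discouraged, subjects may withdraw from the study at any time, with or without reason and without prejudice to further treatment". The consequence carries no exception: "Withdrawn subjects will not undergo any additional follow-up, nor will they be replaced". Data gathered before withdrawal remain available to the analysis. The reason for withdrawal goes into the patient's file, and SAP 2.3.1 summarises reasons by treatment group.

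The primary outcome is the mRS at 90 days (Protocol 6.1.1), scored by blinded assessors from a recorded interview (Protocol 6.1.5). The protocol states "Analyses will be performed based on the intention-to-treat (ITT) principle", and SAP 2.2.1 defines the set: "The ITT population will include all randomized subjects according to ITT principles, regardless of their eligibility and any protocol deviations".

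SAP 2.4.2 deals with deaths: "For subjects who died within the study period, the worst scores will be assigned for all subsequent not-assessed clinical outcome measures", which means mRS 6. For other missing efficacy data it names no method. If much is missing, "the study team will propose and determine the solution before database lock".

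The sample size allows for 5% dropout and 5% crossover (Protocol Synopsis and 7.1, SAP 1.4).

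**The concern.** The intervention is one procedure at baseline and the primary outcome is one score at day 90. Any withdrawal in between costs the primary endpoint, although the contact needed to obtain it is short. The protocol does not have sites ask whether that contact would be acceptable.

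Two things make the gap matter here. Patients and treating physicians know the arm (Protocol 6.1.5), so withdrawal may depend on both arm and clinical course. And the SAP has no stated fallback. A living patient without an mRS has no prescribed handling, and a patient who withdraws and then dies may never receive the mRS 6 that SAP 2.4.2 intends, because nobody is instructed to check vital status.

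**Working it through.** **Inputs from the documents.** Control mRS 0 to 6: 3, 9, 21, 18, 22, 6, 21%; common odds ratio (cOR) 1.43; 920 evaluable for 87% power at two-sided 0.05; 1074 randomised, 537 per arm; final-analysis alpha 0.0482 (Protocol Synopsis, 7.1 and 7.2; SAP 4).

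**1. Reproduce the plan.** Applying cOR 1.43 to the control distribution gives 4.2, 12.1, 25.0, 18.5, 19.6, 4.9, 15.7% in the balloon guide catheter (BGC) arm. The mRS 0-2 rate goes from 33.0% to 41.3%, or +8.3 points against the stated 8.

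Whitehead's proportional-odds formula is N = 12(z_α/2 + z_power)² / [(ln cOR)² × S], where S = 1 − Σp̄³ and p̄ is the mean of the two arms' proportions. Here S = 0.9652 and ln 1.43 = 0.3577.

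- N for 87% power = 12 × (1.960 + 1.126)² / (0.3577² × 0.9652) ≈ 926, against 920 stated.
- Power at 920 = Φ(0.3577 × √(920 × 0.9652/12) − 1.960) = Φ(1.117) = 86.8%, against 87% stated.
- 920 / (0.95 × 0.95²) = 1073.04, which rounds up to 1074. The documents do not state the inflation formula. This one fits, and its crossover part corresponds to shrinking ln cOR by 0.95.

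**2. Power.** Assume that every budgeted dropout is a withdrawal: 0.05 × 1074 ≈ 54, leaving 1020. Recovering half (27, an assumed share) gives 1047. Power = Φ(0.95 × 0.3577 × √(N × 0.9652/12) − 1.976) at alpha 0.0482:

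| Evaluable N | Argument of Φ | Power |
|---|---|---|
| 1020 | 3.078 − 1.976 = 1.102 | 86.5% |
| 1047 | 3.118 − 1.976 = 1.143 | 87.3% |
| 1074 | 3.158 − 1.976 = 1.183 | 88.1% |

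With the heavier dilution of 0.90 (5% crossing over in each arm) the powers are 82.6%, 83.6% and 84.5%. Either way, recovering half gains at most about one point.

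**3. Bias.** These loss patterns are assumptions; the documents give none. Each arm loses 5% (0.05 × 537 ≈ 27 patients). Selective loss removes 5 points pro rata from the named categories, and the rest are divided by 0.95. For example, control mRS 4 becomes (22 − 5 × 22/28)/0.95 = 19.0%. A proportional-odds model is then fitted to the expected proportions, with true cOR 1.43.

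| Who is lost | Fitted cOR |
|---|---|
| Control loses mRS 4-5, BGC at random | 1.35 |
| BGC loses mRS 4-5, control at random | 1.53 |
| Both arms lose mRS 4-5 | 1.45 |
| One arm loses mRS 0-2, the other at random | 1.30 or 1.60 |
| Both arms lose mRS 0-2 | 1.46 |

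With no true effect, the four one-arm patterns give 0.90 to 1.12 instead of 1.00.

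**The case against.** The best defence is the visit schedule. After day 7 or discharge only the 90-day visit remains, and its list contains the mRS, EQ-5D, costs, safety and concomitant medication, with no imaging, laboratory test or vital signs (Protocol 6.2.2 and 6.2.2.4). A patient who withdraws after discharge is therefore mainly declining the contact that the fix would request. A reader might infer that such patients usually object to visits or tests and would accept an interview. No passage supports that, and the number who would agree is unknown. This stands, and it limits the benefit. It does not justify failing to ask.

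Two stronger readings are also tempting.

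- That the protocol discards data. It does not: section 4.3 keeps what was collected before withdrawal. The later score is simply never obtained.
- That the rule contradicts the ITT analysis. It does not: withdrawn patients remain in the set as randomised. Section 4.3 covers only a patient's own withdrawal and does not stop follow-up after crossover, catheter change or protocol deviation. The analysis is incomplete, not inconsistent with its definition.

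Other mitigation is real but partial. Patients judged unlikely to take part in follow-up are excluded (Protocol 4.2, item 11), dropout is budgeted, and the 5% is not split between withdrawal and loss to follow-up. Asking at withdrawal does nothing for patients who cannot be traced, and vital status alone gives no mRS for survivors. Consent wording was not available for this review and may address later contact, but that would not change the absolute rule in section 4.3.

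**Conclusion.** The point holds as a modest design weakness. As written, the protocol forgoes a 90-day mRS, or knowledge of a death, that some withdrawing patients might permit, and the SAP names no method for the resulting gap.

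Power is not the reason to act. The gain is at most about one point even if all 54 budgeted dropouts are withdrawals and half are recovered. Bias is the reason, but 1.35 and 1.53 are upper-end illustrations. They require the whole 5% allowance to be withdrawals, one arm to lose only mRS 4-5 patients and the other to lose patients at random. When both arms lose the same kind of patient, the cOR stays at about 1.45. Recovering only some outcomes would remove only part of any bias. This is a cheap improvement to consider, not a flaw that undermines the trial.

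**What to change.** Amend Protocol 4.3 along these lines: a withdrawing subject or surrogate is asked whether the single 90-day mRS interview, or failing that vital status from records, may still be collected. It is collected only if agreed. If all contact is refused, nothing further is collected. The type of withdrawal is recorded, so that SAP 2.3.1 can report it by arm.

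The cost is protocol and consent wording, one question at withdrawal, and an ethics amendment approved before use (Protocol 11.1). It helps only those who agree and who have not already withdrawn or passed day 90. It does not replace a stated method for missing mRS in SAP 2.4.2, which is still needed for refusals and untraced patients.
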